There is very limited data on which antihypertensive agent provides the best control of blood pressure in the postpartum period. One small randomized controlled trial (n=50) compared oral labetalol and nifedipine extended release for persistent postpartum hypertension in women with no previous therapy (17). The primary outcome was time to blood pressure control, which was not different between the two groups. Interestingly, blood pressure information was only available in 48% of women at 72 hours, 20% women at 1-2 weeks, and 16% of women at 4-6 weeks.

Outside of recommending treatment for postpartum blood pressure that is persistently above 150/100 mm Hg and using labetalol or nifedipine extended release, ACOG does not provide explicit guidance on initial dose of therapy, dose adjustments, duration of therapy, or parameters for discontinuing antihypertensive therapy. Additionally, many women who have gestational hypertension or preeclampsia, will have normalization of blood pressure without medical intervention. There is no data to evaluate spontaneous normalization of blood pressure as compared to women who are prescribed anti-hypertensive therapy for postpartum non-severe postpartum hypertension.

- c) ACC/AHA most recent blood pressure guidelines recommend blood pressure goal of <130/80 mm Hg in non-pregnant adults. No data on if women with hypertensive disorders of pregnancy are meeting this goal at their postpartum visit.

In 2017, the American College of Cardiology and American Heart Association Task Force on Clinical Practice Guidelines released new guidance for the diagnosis and treatment of hypertension which replaced the Joint National Committee 8 recommendations (JNC8) (18). Of note, hypertension was

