classified into 4 stages, and normotensive blood pressure was defined as blood pressure < 130/80 mm Hg. Additionally, the use of blood pressure lowering medication is recommended for primary prevention of cardiovascular disease in adults with no history of cardiovascular disease when blood pressures are >140/90 mm Hg. If adults have a ≥10% risk of 10-year atherosclerotic cardiovascular disease (ACVD) or history of cardiovascular disease, blood pressure lower agents should be initiated if blood pressure ≥130/80 mm Hg. The 10-year ACVD risk will be unknown for most postpartum patients. However, many of our patients will have common risk factors for CVD. Pregestational diabetes affects 3-7% of pregnancies (19). Approximately 32% of reproductive age women ages 20-39 are obese (20). Increasing maternal age should also be a consideration for management of postpartum hypertension, given that older women are increased risk of adverse outcomes postpartum (21). Taken together, more research is needed to optimize treatment of postpartum hypertension especially in light of recent change management of non-pregnant adults.

Design & Procedures

This study is a pilot, open-label randomized controlled trial of postpartum women with hypertensive disorder pregnancy and non-severe, but elevated postpartum blood pressure. Potential study patients will be approached by a member of the study team during the postpartum period of the patient's delivery admission.

Exposures groups will be treated with nifedipine extended release and no treatment for non-severe postpartum hypertension. Patient will be randomized 1:1 fashion. The primary outcome of this study is average systolic blood pressure at 1 week postpartum. Blood pressure will be obtained at a 1-week blood pressure check. Alternatively, women will also be provided blood pressure cuffs and be able to check their blood at home at 1 week and submit result via text. Secondary outcomes will include average diastolic blood pressure at 1 week postpartum, average systolic and diastolic blood pressure at 4 weeks postpartum, percentage of patient with blood pressure < 130/80 mm Hg at 1 week and 4 weeks postpartum, method of feeding, ED/triage visits, increase in blood pressure medication at 1 week postpartum visit, initiation of blood pressure medication at 1 week postpartum visit for patients in the no treatment group, addition of 2nd blood pressure medication at 1 week postpartum visit, and hospital readmission.

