Based on an expected average systolic postpartum blood pressure of 140 mmHg at randomization and standard deviation of 15 points, a sample size of 40 per group is needed to detect a 10 point change in systolic blood pressure with at least 80% power and alpha of 0.05. Assuming a study attrition rate of 20%, an additional 10 subjects per study group will be enrolled. The total goal enrollment is 100 participants (50 in each group) If subject recruitment is lower than expected, we calculated an alternative power calculation. Based on an expected average systolic postpartum blood pressure of 140mmHg at randomization and standard deviation of 15 points, a sample size of 21 per group is needed to detect a 15 point change in systolic blood pressure with 90% power and alpha of 0.05.

Assuming a study attrition of rate of 20%, an additional 4 subjects per study group will be enrolled. The total enrollment using this alternative power calculation 50 (25 in each group).

Statistical analysis plan

Baseline characteristics (demographics, comorbidities, and obstetric history) will be summarized with mean (standard deviation) or n (%) by treatment and control groups. The primary outcome will be presented and compared between two groups using a two-sample t-tests with equal variance. Normality assumption on empirical distribution of the primary outcome will be evaluated. If this assumption is violated, non-parametric Wilcoxon rank sum test will be used. Secondary outcomes will also be summarized and compared between groups using two-sample t-tests with equal variance for continuous outcomes or Chi-square tests for categorical outcomes. A planned, exploratory subgroup analysis will be performed to compare the treatment effect in participants with and without antepartum diagnosis of preeclampsia with severe features. Two-sided tests at $P<0.05$ will be considered statistically significant. All analyses will be performed in SAS 9.4 (SAS Institute Inc., Cary, NC). Statistical support will be provided by [name], MS and [name].

Data & Safety Monitoring

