Subjects in both study groups will be provided with home blood pressure cuffs at discharge. They will be instructed to check blood pressure daily for 1 week postpartum and weekly thereafter. Subjects will be instructed to contact on-call OB providers if they have home blood pressure $< 90/60$ or $>/=160/110$. The contact for the OB triage, OB provider on call will be provided to patients. Subjects will be assessed for potential symptoms of nifedipine extended release at 1 week and 4 weeks postpartum visits. Patients will be referred to or given information for a primary care physician to for continued follow-up outside of the postpartum period.

A Data Monitoring Committee (DMC) will be created to perform regular and timely review of data semi-annually in order to identify early, significant benefit or harm for patients while the trial is in progress. Non-identified safety data will be communicated to the DMC who will then meet to review the data. The DMC will be composed of three faculty members within the Duke University Department of Gynecology and Obstetrics. Individuals who are investigators or co-investigators cannot be members. Members must have no financial, scientific, or other conflicts of interest with the study. All investigators understand that the DMC serves as additional human subject's protection, but does not supplant reporting of significant adverse events to the Duke IRB. The DMC may devise its own stopping rules, and if there are significant numbers of adverse events, the DMC will recommend continuation, modification, or termination of the study after each meeting. This recommendation will be communicated to the Principle investigator who is responsible for reviewing the recommendation and forwarding it to the IRB. All investigators understand that the DMC may recommend their own "stopping rule" if other events occur which indicate a significant risk to study subjects.

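### The primary 1-week systolic comparison is an unadjusted t-test; adjusting for the baseline pressure recorded at entry would gain precision and some protection against uneven loss

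*Combined protocol and SAP*

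**What the plan says.** Design & Procedures defines the endpoint: "The primary outcome of this study is average systolic blood pressure at 1 week postpartum". It is taken at a 1-week check or, alternatively, from a home reading sent by text.

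The Statistical analysis plan gives the method: "The primary outcome will be presented and compared between two groups using a two-sample t-tests with equal variance". If normality fails, "If this assumption is violated, non-parametric Wilcoxon rank sum test will be used". Continuous secondary outcomes use the same t-test. Neither test takes a covariate. The document names no analysis set, missing-data method, sensitivity analysis or repeated-measures model.

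The Sample size calculation assumes an "expected average systolic postpartum blood pressure of 140 mmHg at randomization and standard deviation of 15 points" and concludes that "a sample size of 40 per group is needed to detect a 10 point change in systolic blood pressure with at least 80% power". Attrition of 20% is answered by raising 40 per group to 50.

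Two sources of earlier pressure data are mentioned. Selection of Subjects requires at least two documented elevated readings more than 12 hours postpartum. Data & Safety Monitoring says of women in both arms: "They will be instructed to check blood pressure daily for 1 week postpartum and weekly thereafter". It does not say that these readings are collected as study data.

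**The concern.** A baseline measure of the outcome is on record for every eligible woman, and the primary test does not use it. Leaving it out does not bias a randomised comparison, but it widens the confidence interval whenever baseline and 1-week pressures are correlated.

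The second issue is loss. A t-test with no missing-data rule uses only women who have a 1-week value. Extra enrolment restores their number but not the comparability of the arms. Uneven loss is plausible here: the trial is open-label, the control arm is untreated, only one arm takes a drug with listed side effects, and women see their own readings. The Background also reports an earlier trial with pressure data in only "20% women at 1-2 weeks, and 16% of women at 4-6 weeks". If loss followed pressure differently by arm, the t-test estimate would shift and nothing in the plan would detect or limit that.

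**Working it through.** **Inputs.** From the Sample size calculation and Statistical analysis plan: difference 10 mmHg, SD 15, two-sided alpha 0.05, 40 completers per arm, 20% attrition. Not in the documents, and assumed: the baseline-to-week-1 correlation ρ (0.3 to 0.7) and every loss mechanism below.

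**1. The plan's own figure.** n = 2(1.960 + 0.842)² × (15/10)² = 35.3, so 36 per group (37 with the t distribution). At 40 per group the standard error is 15 × √(2/40) = 3.35 and power is 83.8%, which meets the stated target of at least 80%. Attrition: 40/(1 − 0.20) = 50. The plan's numbers are consistent.

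**2. Precision from baseline adjustment.** Residual SD = 15 × √(1 − ρ²); standard error = residual SD × √(2/40); equivalent gain in sample size = 1/(1 − ρ²).

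| Analysis | Residual SD | SE | Power | Sample-size factor |
|---|---|---|---|---|
| t-test | 15.0 | 3.35 | 83.8% | 1.00 |
| ANCOVA, ρ = 0.3 | 14.3 | 3.20 | 87% | 1.10 |
| ANCOVA, ρ = 0.5 | 13.0 | 2.90 | 92.5% | 1.33 |
| ANCOVA, ρ = 0.7 | 10.7 | 2.40 | 98.5% | 1.96 |

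**3. What a given bias would do.** With 20% lost in each arm, bias in the completers' difference = 0.2 × (between-arm gap in how much dropouts differ from completers). Gaps of 5, 10 and 15 mmHg give 1, 2 and 3 mmHg. Toward the null, these cut t-test power from 83.8% to 75.5%, 65.4% and 54.0%. With no true effect, they raise the 5% error rate to 6.0%, 9.1% and 14.3%.

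**4. Which mechanisms produce bias.** Simulated with 20% loss per arm and a true reduction of 10 mmHg. The log-odds of loss change by 1 per SD where loss is related to pressure. Entries are absolute bias in mmHg; three values are for ρ = 0.3 / 0.5 / 0.7.

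| Loss related to | t-test | ANCOVA |
|---|---|---|
| Baseline or week-1 value, same in both arms | about 0 | about 0 |
| High baseline, controls only | 0.8 / 1.3 / 1.8 | about 0 |
| Baseline, opposite directions by arm | 1.6 / 2.6 / 3.7 | about 0 |
| High week-1 value, controls only | 2.6 | 2.4 / 2.0 / 1.4 |
| Week-1 value, opposite directions by arm | about 5.2 | 4.8 / 4.0 / 2.8 |

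Baseline adjustment removes bias that runs through baseline, and only part of the bias tied to the unseen 1-week value.

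**5. What home readings add.** This assumes 50 enrolled per arm, 20% random loss, and correlations of 0.5 (baseline to week 1), 0.7 (early home mean to week 1) and 0.6 (baseline to home). The simulated standard error is 3.36 for the t-test, 2.87 for baseline ANCOVA and 2.80 with home readings as well. Nearly all the gain comes from the single baseline covariate. If loss depends on early home pressure, a model that has those readings for every woman recovers 10. If loss depends on the week-1 value itself, with slopes of 1 in opposite directions, even that model gives about 12.9 for a true 10.

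**The case against.** The best defence is that an unadjusted t-test in a randomised trial is valid, that 40 completers already give 83.8% power, and that this is a pragmatic pilot. All three are true. They make the t-test acceptable but not the better choice, because the trial is still powered and tested at P<0.05 and adjustment needs only data already recorded.

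The defence also limits the bias argument, and most of that stands. A reader might infer from the 20% attrition, the open-label design and the poor follow-up in the cited trial that the 1-week difference will be biased. The documents do not support that. The 20% is a planning figure and nothing says loss is informative. The cited trial is a different study, comparing labetalol with nifedipine. The instruction to call about very high or low readings is the same in both arms, and a texted reading can supply the 1-week value. Large distortions, such as estimates of 7.5 or 13.8 for a true 10, need loss running in opposite directions in the two arms plus assumed correlations. Loss tied moderately to early home pressure in controls only (slope 0.5 per SD) shifts the estimate by about 1 mmHg. A completers-only analysis is implied by the plan's silence, not written.

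A reader might also infer that a repeated-measures model on the daily readings would solve the problem. That would require those readings to reach the study from women who later drop out. The protocol presents them as safety monitoring and provides for texting only the 1-week result.

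**Conclusion.** The point holds as an avoidable loss of precision and a missing safeguard, not as a demonstrated bias. At the plan's SD, effect and number of completers, baseline adjustment would lift power from 83.8% to between about 87% and 98.5%. The size depends on a correlation the documents do not give. Because entry requires elevated pressure, the baseline range may be narrowed, so the lower end should be taken seriously; even ρ = 0.3 is worth about 10% more patients.

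Bias is about zero if loss works alike in both arms. It is roughly 1 to 4 mmHg if loss runs through baseline differently by arm, and ANCOVA then removes it. It reaches about 5 mmHg if loss follows the unseen 1-week value in opposite directions, which neither baseline nor home readings fully correct. These bias figures rest on assumed mechanisms. The precision gain does not depend on any of them, so the change should be made.

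**What to change.** Make the primary analysis a linear model (ANCOVA) of 1-week systolic pressure on arm and baseline systolic pressure, and state in advance which documented reading, or mean of readings, is the baseline. Use the same approach for 1-week diastolic pressure and the 4-week values, each with its own baseline. Keep the t-test, with its rank-sum alternative, as supporting.

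Add two sensitivity analyses for missing 1-week values. First, where daily home readings have actually been received as study data, use them in a mixed model or in imputation. Second, run one delta-shift analysis in which missing 1-week values are moved by a range of amounts, separately by arm, to show how far the conclusion depends on unseen pressures.

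The cost is SAP wording and modest SAS programming. Baseline pressure is already documented and no extra patients are needed. Receiving the daily readings as study data would need a small addition to the texting procedure, but the primary analysis does not depend on it.

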The treatment of persistently elevated non-severe blood pressure in the postpartum period is the interest of this proposal. In its newest hypertension in pregnancy guidelines, ACOG does not provide any specific guidelines for management of postpartum hypertension. The two most commonly used long-

acting oral anti-hypertensive used for postpartum hypertension are labetalol and extended-release nifedipine.

SIGNIFICANCE

- a) Postpartum hypertension is a significant contributor to severe maternal morbidity and maternal mortality

In the United States, there has been a recent focus on improving maternal mortality and severe morbidity. The maternal mortality rate in the United States has increased from 9.9 per 100,000 births in 1999 to 26.4 per 100,000 births in 2015, making it one of the highest maternal mortality rates among industrialized nations. This increase is most notable among non-Hispanic black women who had a mortality rate of 46 per 100,000 births in 2014. More common, however, is severe maternal morbidity (SMM), which increases the risk for maternal mortality. SMM can be explained as adverse outcomes of the process of labor and delivery that result in significant short-term or long-term consequences to a woman's health. The Center for Disease Control and Prevention defines SMM by 18 indicators commonly identified as peripartum complications. Severe maternal morbidity, like maternal mortality, has also significantly increased over the last 2 decades, from 49.5 per 10,000 births in 1993 to 144.0 per 10,000 births in 2014.

Hypertensive disorders of pregnancy such as preeclampsia and gestational hypertension are strongly associated with SMM including stroke, eclampsia, renal failure, and cardiomyopathy. Studies have shown that women with SMM are significantly more likely to have been diagnosed with a hypertensive disorder of pregnancy .

- b) ACOG does not provide robust guidance on the management of BP in the postpartum period

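### Severe-range pressure, low pressure and nifedipine side effects are monitored but are neither outcomes nor analysed by arm, so harm is compared only indirectly

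*Combined protocol and SAP*

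**What the plan says.** Design & Procedures sets the primary outcome: "The primary outcome of this study is average systolic blood pressure at 1 week postpartum". The secondary outcomes begin with diastolic pressure at 1 week, both pressures at 4 weeks, and the share of women below 130/80 at each time. The list then names "method of feeding, ED/triage visits, increase in blood pressure medication at 1 week postpartum visit". A further item, which applies to one arm only, is "initiation of blood pressure medication at 1 week postpartum visit for patients in the no treatment group". It closes with a second drug being added at that visit and with readmission.

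The statistical analysis plan covers baseline summaries, the primary outcome, one exploratory subgroup analysis and the listed secondary outcomes: "Secondary outcomes will also be summarized and compared between groups", by t-test or chi-square test. It names no safety or adverse-event analysis.

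The harms appear elsewhere. The Risk/Benefit Assessment lists expected drug effects, low pressure among them, and has side effects assessed at every postpartum visit. Data & Safety Monitoring adds: "Subjects will be assessed for potential symptoms of nifedipine extended release at 1 week and 4 weeks postpartum visits". Under the same section both groups receive a home cuff, measure daily for the first week and weekly after that, and are told to call if a reading is below 90/60 or at or above 160/110. De-identified safety data go to a DMC that meets semi-annually; the content of those data is not specified.

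**The concern.** The trial compares a drug with no drug for a condition that, by the protocol's own account, often resolves without treatment. Choosing between the two means weighing low pressure and side effects on the drug against severe-range pressure off it. The plan seeks information on both, then stops short of saying that either will be counted and reported by arm.

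The pressure outcomes do not fill the gap. A mean does not show how many women reached the range that the Background links to stroke. The share below 130/80 does not separate a well-controlled reading from a very low one: read literally, 85/50 meets the criterion. As this is described as a pilot, event rates by arm are also among the figures that a later trial would need.

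**Working it through.** **Step 1: each harm against the plan.** The plan states no harm rate, so there is no figure to reproduce.

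| Harm | Where it is watched for | Listed outcome? | By-arm analysis? | Nearest listed proxy |
|---|---|---|---|---|
| Pressure ≥160/110 | Home call threshold | No | No | Starting medication (controls, 1-week visit only) |
| Pressure <90/60 | Home call threshold; listed drug effect | No | No | ED/triage visits |
| Side effects | Every postpartum visit; symptoms at 1 and 4 weeks | No | No | ED/triage visits, readmission |

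**Step 2: what the proxies can show.**
- *ED/triage visits and readmission* are compared between arms, but no cause is specified. Women are told to call for readings at either extreme, so low pressure on the drug and severe pressure off it can feed the same count and offset each other.
- *Starting medication in controls* is meant to happen only in the severe range, so it is a proxy for that harm. It covers one arm at one visit and allows no contrast.
- *A dose increase or a second drug* presupposes a first drug, so these items describe mainly the treated arm. Both are at the provider's discretion.

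**Step 3: possible size of the unreported difference (illustrative).** Inputs from the sample size section: SD 15, difference 10, 40 evaluable women per arm. Assumptions: normality, a common SD, and one systolic reading per woman. The share reaching 160 is 1 − Φ((160 − mean)/15). The plan's mean of 140 is the value expected at randomization. The follow-up mean without treatment is not given, so a range is shown.

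| Assumed control mean | Control ≥160 | Treated ≥160 (mean 10 lower) | Expected women of 40 |
|---|---|---|---|
| 140 | 1 − Φ(1.33) = 9.1% | 1 − Φ(2.00) = 2.3% | 3.6 vs 0.9 |
| 135 | 1 − Φ(1.67) = 4.8% | 1 − Φ(2.33) = 1.0% | 1.9 vs 0.4 |
| 130 | 1 − Φ(2.00) = 2.3% | 1 − Φ(2.67) = 0.4% | 0.9 vs 0.15 |

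The ratio is about four or more throughout. The absolute counts are small and depend on the assumed mean.

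**Step 4: what 40 or 21 per arm can support.** These are the plan's main and alternative evaluable sizes. Harm rates are assumed. With p̄ the average of p1 and p2, two-sided power at 0.05 is Φ{[|p1 − p2| − 1.96√(2p̄(1 − p̄)/n)] / √([p1(1 − p1) + p2(1 − p2)]/n)}. For 5% vs 15% at n = 40 this is Φ[(0.10 − 1.96 × 0.0671)/0.0661] = Φ(−0.476) = 32%.

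| Assumed rates | Power, n = 40 | Power, n = 21 | n per arm for 80% |
|---|---|---|---|
| 5% vs 15% | 32% | 19% | 141 |
| 5% vs 20% | 53% | 31% | 76 |
| 10% vs 20% | 24% | 14% | 199 |
| 10% vs 30% | 61% | 36% | 62 |

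Estimation is still informative. With no events in an arm, the one-sided 95% upper limit is 1 − 0.05^(1/n): 7.2% at n = 40 and 13.3% at n = 21. If both rates were 10%, the 95% half-width for the difference would be 1.96√(2 × 0.1 × 0.9/n): 13.1 percentage points at n = 40 and 18.1 at n = 21.

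**The case against.** The strongest reply is that harm is not ignored. ED/triage visits, readmission and medication changes are secondary outcomes and can count against either arm. Starting medication in controls is tied to the severe range. The DMC is charged with looking for harm, and significant adverse events go to the IRB. The trial is a pilot with blood-pressure objectives, and no stated analysis becomes invalid.

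Much of this stands, and it rules out three stronger readings that a reader might infer:
- *The trial compares benefit with no harm at all.* The harm-related secondary outcomes contradict this.
- *Untreated women have no measure of severe pressure beyond ED/triage visits and readmission.* Starting medication is such a measure, though limited to one arm and one visit.
- *The outcome list as a whole favours treatment.* Only the pressure outcomes fit that description; visits, readmission and an added second drug can go against the drug.

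Two further cautions stand. The figures in Step 3 ignore diastolic pressure and repeated readings, and the exclusion of women with treated severe-range pressure more than 24 hours after delivery may thin the upper tail. In an open-label trial, symptom reports and submitted home readings may also differ by arm for reasons unrelated to true harm.

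The reply does not supply a by-arm result for the three harms. DMC review is interim oversight, not a reported comparison, and the data it receives are undefined.

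**Conclusion.** The point holds as a gap in outcome definition and reporting. Followed exactly, the plan yields no by-arm count of severe-range pressure, low pressure or side effects, and its indirect comparisons cannot separate them. This rests on the text of the outcome list and the analysis plan, not on a calculation.

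The size is uncertain. The 9.1% versus 2.3% contrast is illustrative because it carries the randomization mean forward to follow-up; lower control means give fewer events. Under every assumed pair of rates in Step 4, power at 40 or 21 per arm is 61% or less, so these outcomes are for estimation only. The primary analysis and the sample size are unaffected. The change is worth making because it improves what the trial can say about harm at little cost.

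**What to change.** Add to the outcome list, as descriptive secondary safety outcomes, the number and percentage of women in each arm with:
- (a) any recorded pressure at or above 160/110;
- (b) any recorded pressure below 90/60;
- (c) any symptom on the Risk/Benefit Assessment list, asked identically in both arms.

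Use the 1- and 4-week visit data and any home readings submitted. State whether the systolic or diastolic value alone is enough for (a) and (b). Report exact confidence intervals and the completeness of home readings by arm, plan no tests, note the open-label reporting caveat, and give the same table to the DMC.

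Do not extend the list to the severe morbidity that the Significance section calls "strongly associated with SMM including stroke, eclampsia, renal failure, and cardiomyopathy". At the rate quoted there for all births, 144 per 10,000, about 40 × 0.0144 = 0.6 women per arm would be expected, so the rows would be nearly empty.

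Separately, the level at which controls may start medication is written as above 160/110 in Design & Procedures and as at or above it in Study Interventions. The two passages must be reconciled.

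The cost is outcome wording, one table and some data entry, with no extra patients or visits. The documents mention no home log and describe texting only a 1-week result, so collecting every home reading to 4 weeks would be new data capture. The proposal needs only the readings that women submit.

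### Does asking the DMC to look for early benefit, with no efficacy stopping rule, undermine the single final test at 0.05?

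*Combined protocol and SAP*

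**What the plan says.** The Data & Safety Monitoring section sets up a DMC for "regular and timely review of data semi-annually", with the stated purpose "in order to identify early, significant benefit or harm for patients while the trial is in progress". On what the committee receives, it says: "Non-identified safety data will be communicated to the DMC who will then meet to review the data". No other type of data is named.

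Two sentences deal with stopping. One begins "The DMC may devise its own stopping rules, and if there are significant numbers of adverse events" and goes on to say that the committee recommends continuing, modifying or ending the study after each meeting. The other lets it recommend a rule of its own "if other events occur which indicate a significant risk to study subjects". Recommendations go to the principal investigator, who reviews them and forwards them to the IRB.

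The Statistical analysis plan section describes one between-group comparison of the primary outcome, average systolic pressure at 1 week, by a two-sample t-test. Its significance rule is "Two-sided tests at $P<0.05$ will be considered statistically significant". It mentions no interim analysis, boundary or division of alpha. Design & Procedures says: "This study is a pilot, open-label randomized controlled trial".

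**The concern.** The stated purpose and the working arrangements do not match. The committee is asked to find early benefit, but is given no efficacy data, no criterion for benefit and no interim significance level. The clause allowing it to devise its own stopping rules is not limited to harm, and nothing in the plan says that stopping for efficacy is excluded.

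If the committee did compare mean blood pressure between arms at each meeting and stopped at the only level the plan mentions, P<0.05, two things would go wrong. The chance of a false positive would exceed 5%, and trials stopped early would overstate the effect.

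**Working it through.** **1. The planned design is a fixed one.** Inputs from the sample size calculation: difference 10 mmHg, SD 15, two-sided alpha 0.05, power at least 80%, 40 evaluable per group, 20% attrition.

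- n per group = 2 × (1.960 + 0.842)² × 15² / 10² = 35.3, so 36 (37 with the t distribution).
- At 40 per group the standardised difference is 10 / (15 × √(2/40)) = 2.98. Power is Φ(2.98 − 1.96) = 84.6%, or 83.8% by noncentral t.
- 40 / (1 − 0.20) = 50 per group, the stated enrolment.

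The stated power of at least 80% is met. The calculation contains no allowance for interim looks, which agrees with an analysis section that plans none.

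**2. What unadjusted efficacy looks would do.** The number of reviews and any interim level are not in the documents. Assume equally spaced looks, the last being the final analysis, each at two-sided P<0.05, under no true difference.

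| Total looks | Early stop for benefit only: overall error | of which false benefit | Early stop in either direction: overall error |
|---|---|---|---|
| 2 | 6.7% | 4.2% | 8.3% |
| 3 | 7.9% | 5.4% | 10.7% |
| 4 | 8.8% | 6.3% | 12.6% |
| 5 | 9.6% | 7.1% | 14.2% |

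For two looks, the test statistics at halfway and at the end have correlation √0.5 = 0.707. The either-direction figure is 1 − P(|Z₁| < 1.96 and |Z₂| < 1.96) = 8.3%. With early stopping for benefit only, false benefit is 4.2% and false harm at the final test remains 2.5%, which together give 6.7%.

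If the true difference were 10 mmHg (SD 15), one such look at 20 per group would stop about 54% of trials, and those trials would report 13.4 mmHg on average.

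**3. What the plan's own arrangements do.** If the committee sees safety data and no efficacy test is made before the end, the primary outcome is tested once and the two-sided error is 5%. Stopping because the drug looks worse leaves false claims of benefit at 2.5% for any number of looks.

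Here blood pressure is both the outcome and a safety signal, so a harm stop could also arise from too many severe readings in untreated controls, and that would favour the drug. Assume mean 140, SD 15, 40 per group, one halfway look, and a stop if controls have at least k more patients than the drug group with systolic pressure of 160 or above. For k from 5 down to 2, false claims of benefit are about 2.6% to 2.9% instead of 2.5%.

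**4. The texts side by side.** The figures in step 2 need three things: blood pressure compared by arm at the interim reviews, a P<0.05 efficacy rule, and a stop made on it. The monitoring section names only safety data and gives no efficacy rule. The analysis section plans no interim comparison. What remains is one word in a purpose clause and one permissive clause without a stated scope.

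**The case for a change.** The strongest case for a change is that the text does not confine the committee to safety. It does not say that safety data are all it will get, and the permission to devise stopping rules is open-ended. Since home readings below 90/60 or at or above 160/110 prompt a call to the obstetric team, safety data could reasonably include blood pressure, which is the primary outcome. Non-identified may mean without names or without arm labels. A rule for benefit devised during the trial would leave the final 0.05 without a clear meaning, and a sentence of clarification costs no patients.

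Much of this stands. The wording is loose, and an efficacy stop is neither allowed nor excluded in terms. But an open permission is not a planned efficacy analysis, and the committee only recommends. Leaving stopping rules to an independent committee is a common arrangement.

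The tightest clarification, a bar on any interim comparison of blood pressure between arms, would carry a cost of its own. With an untreated control group, the committee may need exactly that comparison to see harm from non-treatment. A formal boundary of P<0.001 at interim reviews would hold the error at 5.0% to 5.1%, but it would regulate an analysis that nobody has planned.

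**Conclusion.** The concern does not call for a change. The mention of benefit is at odds with the rest of the monitoring section, but what is to be done is clear enough: safety data go to the committee, recommendations respond to adverse events or risk, and the primary outcome is tested once at two-sided 0.05. On that reading the error rate is 5%. Safety stops driven by severe blood pressure in controls would move false claims of benefit only from 2.5% to 2.9% at most, under the assumptions shown.

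The larger figures, 6.7% or 8.3% with one extra look and up to 9.6% or 14.2% with five looks in all, apply only if the committee tests blood pressure by arm at P<0.05 and stops on the result. The documents provide for neither step, and they give no accrual period from which to count reviews.

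This is missing detail in a pilot trial that a committee and analyst would fill sensibly. Should the trial in fact stop early on blood pressure results, the report would have to say so and the final P value would need to be read accordingly. That possibility does not make the planned test unsound.
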